### 3. STUDY DESIGN

A 6-month, single center randomized controlled trial to study the effects of dietary interventions on improving endothelial health in South Asian patients with diabetic nephropathy. In total 90 South Asian patients with type 2 diabetes and proven microalbuminuria between 18-75 years of age will be recruited at general practitioner centers in the The Hague region. Eligible patients will be included for a period of 6 months. Patients will be randomly assigned to receive the fasting mimicking diet, food supplement or placebo for a period of 3 months. The primary endpoint is an improvement of the Microvascular Health index after 3 months in the diet group compared to the placebo group and in the food supplement group compared to the placebo group, measured with SDF-imaging. After 6 months, which is 3 months after stopping with the interventions, patients will also return for a follow-up measurement to investigate possible legacy effects of each intervention.

The food supplement and placebo arm will be double blinded. The placebo arm will also be used as a control group for the FMD arm.

Study procedures will take place at the practice of the general practitioner and will be performed by LUMC research staff. The general practitioner will not perform any of the study procedures. Flow chart I gives an overview of the study design and time points for study visits.

Flow chart I

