### 5.2 Use of co-intervention

Patients included in the study can be on standard diabetic care consisting of oral hypoglycemic drugs or insulin. During the study, the diabetes medication will/can be altered, which is explained in paragraph 5.3. Included patients can also be on standard antihypertensive care with antihypertensive medication. The antihypertensive drugs can be altered during the study and is left to the discretion of the investigator. However, preferably RAAS inhibitors will not be altered during the study as this can influence heparanase activity and albuminuria.

Other co-medication is allowed with the exception of immunosuppressive (such as prednisolone) and low molecular weight heparin. Use of co-medication should be documented.

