#### 7.1.2 Secondary study parameters/endpoints

Secondary endpoints include;

- Albuminuria: urinary excretion of albumin, using albumin/creatinine ratio in mg/mmol.
- Inflammation: urinary heparanase and MCP-1 expression, serum C-reactive protein, and MCP-1 levels.
- Metabolic response: fasting glucose, HbA1c, C-peptide, IGF-1, total cholesterol, LDL cholesterol, HDL cholesterol, triglycerides levels, body weight, waist circumference, waist-to-hip ratio and systolic blood pressure.
- Identifying specific urinary heparan sulfate domains.

To evaluate the legacy effects of the interventions, the primary and secondary parameters will also be assed three months after stopping the intervention.

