#### **7.6 Follow-up of subjects withdrawn from treatment**

No follow up will be done for subjects who are withdrawn from the study except for regularly follow up at the general practitioner. In case of withdrawal because of an adverse event, subjects are followed as described in paragraph 9.4.

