## 9. STATISTICAL ANALYSIS

### 9.1 Primary study parameter

SPSS will be used for all statistical analysis. Data analysis will be performed based on the intention to treat principle. Patients will be included in the analyses according to the treatment to which they were randomised.

The primary endpoint Microvascular Health index (MHI) will be summarized in mean with standard deviation or median with interquartile range. The effect within the group between baseline and 3 months is tested using a paired Student's t test (two-tailed). Differences in improvement of the MHI between baseline and 3 months between the FMD group and the placebo group and the food supplement and placebo group will be tested with an independent Student's t test.

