### 9.2 Secondary study parameters

The categorical data will be summarized by the frequencies and percentages and tested within the group between baseline and 3 months using a Pearson's Chi-squared test. The continuous data will be summarized in mean with standard deviation in case of normal distribution or median with interquartile range in case of non-normal distribution. A paired two-tailed Student's t test or Wilcoxon signed rank test will be used to calculate the effect within the group between baseline and 3 months.

Differences in outcomes between the groups (diet vs placebo and supplement vs placebo) will be tested with a Student's t test for normally distributed data or Mann-Whitney *U* test for non-normally distributed data.

A paired two-tailed Student's t test or Wilcoxon signed rank test for differences of the primary and secondary parameters between baseline and 6 months within the group will be used to evaluate the legacy effect of the interventions 3 months after stopping with the intervention.

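### The 6-month legacy effect is assigned only a within-arm paired test; no placebo comparison at 6 months is specified for MHI, and for the secondary parameters the text is unclear

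*Combined protocol and SAP*

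**What the plan says.** Four places bear on this point.

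- **Section 7.1.2** sets up the 6-month assessment without naming a comparator: "To evaluate the legacy effects of the interventions, the primary and secondary parameters will also be assed three months after stopping the intervention". The summary and section 3 also announce it. The objectives in section 2 do not include it; they are framed at 3 months.
- **Section 9.1** gives the between-group MHI test and dates it: "Differences in improvement of the MHI between baseline and 3 months between the FMD group and the placebo group", and likewise for supplement against placebo, by an independent t test.
- **Section 9.2** has a between-group sentence without a time point: "Differences in outcomes between the groups (diet vs placebo and supplement vs placebo) will be tested with a" t test or Mann-Whitney test. The sentences before it concern 3 months; the one after it concerns 6 months.
- **Section 9.2** then names the only analysis tied to the legacy effect, a paired t test or its Wilcoxon counterpart, described as "for differences of the primary and secondary parameters between baseline and 6 months within the group will be used to evaluate the legacy effect".

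The control data will exist. Section 3 says "The placebo arm will also be used as a control group for the FMD arm", and the summary and section 10.3 place SDF imaging, blood and urine at three time points in every arm, the last at 6 months.

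**The concern.** The legacy sentence ascribes an effect to the interventions but tests only whether an arm's mean at 6 months differs from its own baseline. That change also contains natural course, effects of taking part in a trial, and co-medication changes that occur alike in all arms. Such changes are possible here. Section 5.2 says "The antihypertensive drugs can be altered during the study and is left to the discretion of the investigator", and the month-end rule in section 5.3 lets glucose-lowering drugs be altered in every arm.

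Two errors can follow. A change shared with placebo can be reported as a legacy effect. Conversely, an active arm that holds steady while placebo worsens can be reported as having none. The placebo arm gets its own paired test, but the plan does not say how the three results are to be read together, and setting two p-values side by side is not a test of their difference. At 3 months the plan gives MHI both a within-group and a between-group test; at 6 months it specifies only the within-group one.

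**Working it through.** **Inputs from section 4.4:** 23 per group after dropout, SD of the MHI improvement 0.41, difference 0.35, two-sided alpha 0.05.

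**Assumptions, because the documents give no figure:** the SD of 0.41 also holds for the 6-month change; all arms share a 6-month change (drift) of a chosen size; arms are independent.

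**1. The plan's own figure.** Two-sample t test, 44 degrees of freedom, noncentrality 0.35 / (0.41 × √(2/23)) = 0.35 / 0.1209 = 2.895. Power is 80.8% with 23 per group and 79.0% with 22. The stated 80% with 23 per group is reproduced.

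**2. Paired test in one arm, no difference from placebo.** 22 degrees of freedom, noncentrality = drift / (0.41/√23) = drift / 0.0855. Let p be the probability that a given active arm is significant.

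| Assumed drift (MHI units) | Given active arm significant, p | At least one of two active arms, 1 − (1 − p)² | Active significant and placebo not, p(1 − p) |
|---|---|---|---|
| 0 | 5% | 9.75% | 4.75% |
| 0.05 | 8.7% | 16.6% | 7.9% |
| 0.10 | 20.1% | 36.2% | 16.1% |
| 0.15 | 38.9% | 62.7% | 23.8% |
| 0.20 | 60.9% | 84.7% | 23.8% |

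The third column includes the multiplicity of testing two arms, so its reference value is 9.75%. The last column shows that reading the placebo p-value alongside does not cure the problem.

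A simulation of 200,000 trials at drift 0.15 gave 39.2%, 62.9% and 24.0% for the three columns. A between-arm t test on the change rejected in 4.9%, its nominal level.

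**3. Sensitivity to the SD.** At drift 0.20 the per-arm figure is 86.3% if the SD is 0.30 and 33.4% if it is 0.60.

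**4. The reverse case.** Suppose placebo worsens by 0.35 and the active arm is stable. The active arm's paired test is significant in 5% of trials; the between-arm test is significant in 80.8%.

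**5. Precision of the two estimates.** The 95% CI half-width within an arm is 2.074 × 0.0855 = 0.177. Between arms it is 2.015 × 0.1209 = 0.244. Between-arm power at 23 per arm is 80.8% for a difference of 0.35, 52.5% for 0.25 and 29.4% for 0.175.

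**The case against.** The strongest reply is that a 6-month placebo comparison may be intended. Section 7.1.2 lists the 6-month MHI under the secondary endpoints, and the between-group sentence in 9.2, headed for secondary parameters, has no date. On that reading it could cover MHI at 6 months too. This is inference. The next sentence names the primary parameter, 6 months and a within-group test, and nothing specifies the other comparison. If it is intended, it still has to be written down.

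Three further points have some force.

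- **The drift is hypothetical.** The documents give no placebo drift and no 6-month SD, and 0.20 is 0.20/0.35 = 57% of the planned difference. The figures show how the test behaves, not what to expect. The flaw does not depend on them.
- **Not every drug change is shared.** The alterations during the diet days in section 5.3 apply to the FMD arm only. Comparison with placebo would not remove their influence; it removes only what the arms have in common.
- **The legacy effect is not an objective in section 2.** That limits how much rests on it, and the placebo data remain available for a later comparison. But the effect is announced in the summary, the design and the endpoints, and a comparison chosen after the data are seen carries less weight.

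**Conclusion.** The concern holds. For MHI, no comparison with placebo at 6 months is specified. For the secondary parameters it is unclear whether one is. The named within-arm test cannot support a statement about the effect of the interventions.

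If all arms share a change of 0.10 to 0.20 MHI units and neither intervention differs from placebo, a given active arm appears to show a legacy effect in about 20% to 61% of trials, against a nominal 5%; at a shared change of 0.05 it is about 9%. These figures rest on an assumed drift, on the 3-month SD carried over to 6 months, and on 23 completers per arm. That within-arm change does not isolate the intervention rests on none of them. The point should be fixed, but it leaves the 3-month primary comparison intact.

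**What to change.** Replace the legacy sentence in section 9.2 with wording such as:

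> The legacy effect is the difference between FMD and placebo, and between supplement and placebo, in the change from baseline to 6 months (T5), for MHI and the secondary parameters, reported with a 95% confidence interval.

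An independent t test on the change, as section 9.1 already uses at 3 months, is enough to remove shared drift. Analysing the 6-month value adjusted for baseline (ANCOVA) is preferable for precision but not essential to the correction. Add the time point or time points to the undated between-group sentence in 9.2, and report within-arm changes as descriptive.

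**Cost.** No new visits, samples or patients are needed. The interval is wider (half-width 0.24 against 0.18 within an arm), and power is limited for differences below 0.35. Numbers at 6 months may also fall short: section 7.6 says "No follow up will be done for subjects who are withdrawn from the study", apart from usual care by the general practitioner. Section 7.5 permits replacement of some drop-outs in the first two and a half months, with the aim of 23 completers per group, but does not cover later losses. The report should therefore give the number analysed per arm at 6 months and should not take a non-significant difference as evidence that there is no legacy effect.

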### 9.3 Other study parameters

Demographic data and other baseline characteristics will be summarised using descriptive statistics. The main analyses will also be performed in a priori defined subgroup analyses such as age at baseline, smokers vs non-smokers ect.

Additional explorative analyses involve the analysis of prognostic and predictive factors for achieving the primary or secondary endpoint, this will be investigated by using logistic regression. The level of significance for all tests will be set at  $p<0.05$ .

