#### **4.4 Sample size calculation**

The primary outcome will be improvement of the Microvascular Health Index after 3 months. The sample size is chosen according to a pilot study with 13 healthy volunteers receiving the food supplement Endocalyx™ for 3 consecutive months. After 3 months, a 31% improvement in Microvascular Health Index was demonstrated, expressed in a significant increase of the MHI from 1.05 at baseline, to 1.38 at 3 months (improvement of 0.33).

Group sample sizes of 23 per group achieve 80% power to detect a difference of 0.35 between the null hypothesis that group improvement means are 0.0 and the alternative hypothesis that the improvement mean of group 2 or 3 is 0.35 with estimated group standard deviations of 0.41 with a significance level (alpha) of 0.05000 using a two-sided two-sample t-test. If we anticipate a 25% drop out rate per group, we will need 30 patients per group.

Therefore, we decided to enrol a total number of 90 patients in this study.

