#### **7.5 Replacement of individual subjects after withdrawal**

The sample size calculation for this study is given in paragraph 4.4. A 25% protocol violator and/or drop-out rate is taken into account. Therefore an inclusion of 30 subjects per study group is aimed. However, drop-outs from this study that occur during the first 2,5 months because of schedule problems, pregnancy or non-diabetic medical reasons may be replaced in order to reach 23 subjects per study group to complete the study. If a subject discontinues from the study prematurely the reason must be fully evaluated and recorded appropriately in

source documentation and the eCRF. If the subject is being withdrawn because of an AE, that AE must be indicated as the reason for withdrawal.

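### The main t tests are repeated within an open list of subgroups and no treatment-by-factor interaction is named; if the planned effect is real and uniform, the chance that exactly one of two subgroups is significant is about 50%.

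*Combined protocol and SAP*

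**What the plan says.** Section 9.3 (Other study parameters) plans the subgroup work in one sentence: "The main analyses will also be performed in a priori defined subgroup analyses such as age at baseline, smokers vs non-smokers ect". The main analyses are those of section 9.1: a paired t test within each arm, and comparisons of the change in MHI between each active arm and placebo. For the supplement, the wording is that the "food supplement and placebo group will be tested with an independent Student's t test"; the diet comparison uses the same test. On the threshold, section 9.3 says: "The level of significance for all tests will be set at" p<0.05.

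Section 9.3 also plans exploratory logistic regression on prognostic and predictive factors for reaching the primary or a secondary endpoint. It names no treatment-by-factor term. The document gives no closed list of subgroup factors, no age cut-off, no adjustment for the number of subgroup tests and no rule for interpreting their results.

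**The concern.** Whether the diet or the supplement works differently in smokers and non-smokers, or in younger and older patients, is a question about the difference between two treatment effects. Two separate p-values do not estimate that difference. In a trial of this size each subgroup test has moderate to low power, so one significant and one non-significant result can easily arise when the effect is the same in both subgroups. A report could then state a benefit confined to one subgroup while following the plan as written.

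The list is called a priori but gives only two examples and is left open, and age has to be cut somewhere before a t test can be run within age groups. The number of chances for such a pattern is therefore not fixed by the document.

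**Working it through.** **Inputs (section 4.4).** "Group sample sizes of 23 per group achieve 80% power to detect a difference of 0.35"; "estimated group standard deviations of 0.41"; "with a significance level (alpha) of 0.05000 using a two-sided two-sample t-test". On enrolment: "If we anticipate a 25% drop out rate per group, we will need 30 patients per group". Section 7.5 repeats the 30 per group.

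**The plan's own figure.** For n per arm, the noncentrality is d / (SD × √(2/n)) with 2n − 2 degrees of freedom. With n = 23: 0.35 / (0.41 × √(2/23)) = 2.895 on 44 df, critical value 2.015, power 80.8%. With n = 22 power is 79.0%. The stated 23 per group is reproduced. (23/0.75 = 30.67 would round up to 31, not 30, which is immaterial here.)

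**Discordant subgroup results under one common effect.** The two subgroups contain different patients, so their tests are independent. With powers p1 and p2,

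P(exactly one significant) = p1(1 − p2) + p2(1 − p1).

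The documents give neither smoking prevalence nor an age cut-off, so the splits below are assumptions.

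For 23 per arm split 11/12, at effect 0.35:
- n = 11: noncentrality 2.002, 20 df, power 0.478
- n = 12: noncentrality 2.091, 22 df, power 0.516
- exactly one: 0.478 × 0.484 + 0.516 × 0.522 = 0.50; both 0.25; neither 0.25

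Other splits at effect 0.35:

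| Per arm | Split | Powers | Exactly one significant |
|---|---|---|---|
| 23 | 5/18 | 0.222, 0.701 | 61% |
| 30 | 15/15 | 0.617, 0.617 | 47% |
| 30 | 9/21 | 0.398, 0.770 | 55.5% |

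**Dependence on the true effect (11/12 split).**

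| True effect in both halves | Powers | Exactly one | Neither |
|---|---|---|---|
| 0.35 | 0.478, 0.516 | 50% | 25% |
| 0.25 | 0.275, 0.298 | 41% | 51% |
| 0.175 | 0.159, 0.170 | 27.5% | 70% |
| 0 | 0.05, 0.05 | 9.5% | 90% |

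**Both placebo comparisons together (simulation, 4,000 runs, 23 per arm, even split on average, effect 0.35 in both active arms, shared placebo).** At least one discordant pair occurs in about 72% of trials with one factor and 88% with two. The numbers of factors are assumed.

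**The alternative.** In the same simulations, a test of the arm-by-factor interaction at 0.05 rejected in 4.6% to 5.3% of trials per factor and comparison when the effect was uniform, whether that effect was 0.35 or zero. Its power for a true difference of 0.35 between two equal halves follows from SE = 0.41 × √(4/n), with n patients per arm and half:
- 23 per arm (n = 11.5): SE 0.242, 42 df, power 29%
- 30 per arm (n = 15): SE 0.212, 56 df, power 37%

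**The case against.** **The 50% is conditional.** It requires the full planned effect to be present and equal in both subgroups. That effect was chosen from a pilot in 13 healthy volunteers, so a smaller one in these patients is plausible. A reader might infer that the plan has a coin-toss chance of a spurious subgroup finding even if the treatments do nothing. The documents do not support that: with no effect, the figure is 9.5% per factor and comparison. Nor is a split result always the most likely outcome. For the 11/12 split it is at 0.35, but at 0.25 and below it is more likely that neither subgroup is significant. This objection stands and limits the claim.

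**Section 9.3 may already cover effect modification.** Predictive factors could be meant as treatment-by-factor effects. The sentence names no such term, however, so it cannot be counted as a planned interaction test. It would be too strong to say that interaction is certain never to be examined; what can be said is that no interaction term is named.

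**The analyses are secondary, and the factors are described as set in advance.** They stand under other study parameters, and the next sentence calls the additional analyses exploratory, which may be meant to include the subgroups. The text does not say that subgroup results will be compared or used to claim different effects. Nor does it show an intention to add factors after seeing data; the open ending may be loose drafting. What can be shown is that the list and the age cut-off are not stated, and that the subgroup tests carry no exploratory label.

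**The interaction test has limits.** Its power is low, and false positives still accumulate: in the simulation with 23 per arm and effect 0.35, at least one interaction was significant in 8.9% of trials with one factor and two comparisons, and in 16.9% with two factors. The corresponding figures for discordant subgroup tests are 72% and 88%. This is a reason for an exploratory label and for reporting intervals. It does not make separate tests preferable.

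**Conclusion.** The concern holds in a conditional form. Repeating the main t tests within subgroups cannot show effect modification, and section 9.3 names no analysis that could. If the planned effect of 0.35 (SD 0.41) is real and uniform, exactly one of two halves is significant with probability of about 50% per factor and comparison with 23 per arm, 47% with 30 per arm, and 56% to 61% under the assumed uneven splits. At smaller effects the figure falls, down to 9.5% when there is no effect. Even that exceeds the roughly 5% of an interaction test.

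The figures rest on normally distributed change scores with a common SD of 0.41, and on assumed split sizes. The consequence is confined to the interpretation of subgroup results. The primary comparisons are not affected.

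**What to change.** In section 9.3:

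- For each factor, fit one model of the primary MHI outcome with arm, factor and arm × factor. The change score already used in section 9.1 can serve as the outcome.
- Report the interaction estimate with its 95% CI for each active arm against placebo. Base any statement about subgroup differences on that estimate and not on within-subgroup p-values.
- Replace the open list by a closed one, fixed before database lock. Keep age continuous, or fix its cut-off in advance.
- Label the subgroup results exploratory.

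The cost is a change of wording and one extra model term per factor. No additional patients, visits or measurements are needed. The low power of the interaction tests, about 29% to 37% for a difference of 0.35, becomes visible to readers.

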## 7. METHODS

### 7.1 Study parameters/endpoints

#### 7.1.1 Main study parameter/endpoints

The primary endpoint is to improve the endothelial microvascular health expressed by an improvement in Microvascular Health Index between baseline and 3 months of treatment in South Asian patients with type 2 diabetes mellitus through:

1. The fasting mimicking diet in comparison to the placebo.
2. The endocalyx food supplement in comparison to the placebo.

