### **SDF imaging**

Sidestream dark field (SDF) imaging is a non-invasive technique that measures the endothelial glycocalyx with a handheld camera that visualizes the sublingual microvasculature. The CE-marked camera is put under the tongue of the patients and measures in total about 3000 vascular segments in the sublingual vessels. The investigator moves the camera to a different location in the mouth until the total amount of frames necessary is determined automatically. This takes about 2-4 minutes.

The camera uses green LED light to detect the hemoglobin in red blood cells and measures lateral red blood cell (RBC) movements, RBC filling percentage, vessel density, and local vascular perfusion efficiency. These parameters reflect the endothelial glycocalyx health status and are affected if the glycocalyx layer is impaired [32, 33]. The image acquisition is automatically mediated through the Glycocheck software (Glycocheck BV, Maastricht, the Netherlands), which combines these parameters and calculates the Microvascular Health Index (MHI). This index ranges from 0.00 to 10.00 with a score between 0.00 – 1.00 reflecting a clinically perturbed glycocalyx and perfusion in the microvasculature, a score between 1.00 – 2.00 a less than average health of the microvasculature, 2.00 – 3.00 an average microvascular health, between 3.00 and 5.00 an above average and a score above 5.00 a good functional microcirculation with adequate endothelial glycocalyx coverage and flow mediated adaptation.

In addition, capillary tortuosity will be determined by placing the SDF camera in four quadrants of the inner lip (duration about 1-2 minutes): the upper right quadrant, upper left quadrant, lower right quadrant and lower left quadrant. From these collected frames, the

capillary tortuosity will be assessed by scoring the number of twists per capillary in the capillaries in the field of view per image. The number of twists will be stratified as 0: no twists (or pinhead capillaries) to 4: four or more twists, described by Djaberi et al. [53] The overall tortuosity score per subject will be determined by selecting the most frequent tortuosity score in the 12 studied microcirculatory imaging areas (3 microcirculatory imaging areas per quadrant).

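### Section 9.3 plans exploratory logistic regression for endpoints that are nearly all continuous, states no responder rule, and would discard at least about 36% of the information

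*Combined protocol and SAP*

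**What the plan says.** Section 9.3 of the combined protocol and SAP introduces this work as exploratory: "Additional explorative analyses involve the analysis of prognostic and predictive factors". The same sentence goes on to give the target and the method: "prognostic and predictive factors for achieving the primary or secondary endpoint, this will be investigated by using logistic regression". No outcome coding, cut-off or model terms are given. The section sets significance at p<0.05 for all tests.

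The endpoints are described elsewhere:

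- **Primary endpoint (7.1.1).** It is "an improvement in Microvascular Health Index between baseline and 3 months of treatment", with no minimum size.
- **Its scale (7.3, SDF imaging).** "This index ranges from 0.00 to 10.00". That section and section 1 attach descriptive labels to bands of the index, but nothing uses a band as a response criterion.
- **Its analysis (9.1).** It is treated as a continuous change and compared by t test: "Differences in improvement of the MHI between baseline and 3 months between the FMD group and the placebo group", and likewise for the supplement against placebo.
- **Secondary endpoints (7.1.2).** Nearly all are continuous laboratory, anthropometric or blood-pressure measures, for example "Albuminuria: urinary excretion of albumin, using albumin/creatinine ratio in mg/mmol". No response threshold is attached to any of them. The exception may be "Identifying specific urinary heparan sulfate domains", whose measurement scale is not stated.

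**The concern.** As written, 9.3 cannot be run until someone decides, endpoint by endpoint, which patients count as having achieved it. The plan neither states that rule nor says when it must be fixed. Two things follow.

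First, whether a factor reaches p<0.05 can depend on where the line is drawn. Second, any line discards information that 9.1 and 9.2 keep, in a trial aiming for 23 completers per arm.

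A further point is the word *predictive*. A prognostic factor relates to outcome whatever the treatment, while a predictive factor changes the treatment effect. Separating the two takes an arm-by-factor term, and 9.3 does not say whether the model will contain one.

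What is at stake is the quality of hypothesis generation, not the trial's main conclusion.

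**Working it through.** **Inputs from section 4.4.** Difference 0.35, SD 0.41, two-sided alpha 0.05, 80% power, 23 evaluable patients per group; 3 × 23 = 69 completers.

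**Assumptions not in the documents.** A normal outcome, the responder share or cut-off, and the factor–outcome correlation (range 0.2 to 0.4).

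**1. The plan's own figure.** The normal approximation gives n = 2(1.960 + 0.842)² × 0.41²/0.35² = 21.5, so 22 per group. Exact t-test power is 79.0% at 22 and 80.8% at 23. The stated 23 reproduces.

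**2. Information kept after dichotomising a normal outcome.** With responder share p, cut-off c at the matching normal quantile and normal density φ, efficiency relative to the continuous analysis is φ(c)²/[p(1 − p)].

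| Responder share | Calculation | Kept | Lost |
|---|---|---|---|
| 50% | 0.3989²/0.25 | 0.637 (= 2/π) | 36% |
| 30% | 0.3477²/0.21 | 0.576 | 42% |
| 20% | 0.2800²/0.16 | 0.490 | 51% |

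The median split is the best case. Even there, 69 × 0.637 ≈ 44, so 69 patients carry the information of about 44.

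**3. The change-above-0 reading, on the plan's own inputs.** This uses the arm comparison because the plan gives an effect size for it. With placebo mean 0, active mean 0.35 and SD 0.41, the responder proportions are 0.500 on placebo and Φ(0.35/0.41) = 0.803 on active treatment. For 80% power:

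n = [1.960√(2 × 0.652 × 0.348) + 0.842√(0.500 × 0.500 + 0.803 × 0.197)]²/0.303² ≈ 38 per arm, against 22 for the continuous outcome.

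Efficiency is 22/38 = 0.58, a loss of about 42%. Power at 23 per arm is about 58%. The same calculation needs 35 per arm at the midpoint cut of 0.175 (37% lost) and 46 at a cut of 0.50 (52% lost).

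**4. Power to detect one continuous factor.** Simulation with 69 patients, linear regression against a logistic likelihood-ratio test at 5%:

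| Assumed correlation | Linear | Logistic, median split |
|---|---|---|
| 0.2 | 39% | 27% |
| 0.3 | 73% | 54% |
| 0.4 | 94% | 77% |

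At 0.3 with 30% responders, logistic power is about 50%. Repeat runs, the largest with 10,000 replicates, moved these figures by about two percentage points at most.

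**5. What an open cut-off could do.** Under no true association, taking the best of five cut-offs between the 30th and 70th percentiles gives p<0.05 in roughly 14% to 16% of simulated trials, depending on the test used, instead of 5%. This shows why the rule should be fixed; it does not describe anything the plan proposes.

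**6. Power of an interaction test.** With factor and residual scaled to SD 1, the difference between two arms' slopes has standard error about √(2/23) = 0.295. For an assumed slope difference of 0.30, z = 0.30/0.295 = 1.02 and power is about Φ(1.02 − 1.96) ≈ 17%.

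**The case against.** The strongest reply is that the work is exploratory. The primary tests, the secondary tests and the sample size do not depend on it, and the trial was never powered to find predictors. That stands, and it limits how much the point matters.

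The second reply is that a responder rule is implicit. Section 7.1.1 speaks of improvement and section 2 words the secondary objectives directionally, so achieving an endpoint could simply mean moving the right way. This reading is available before any data and is not arbitrary. A reader might infer that the investigators intend to choose cut-offs after seeing the results; the documents do not say so. What stands is that the rule is unwritten, and that the change-above-0 reading still loses about 42% on the plan's own inputs.

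Third, a reader might infer that the plan omits the interaction term and so cannot separate prognostic from predictive factors. Section 9.3 lists no model terms at all, and a logistic model can carry an arm-by-factor term. The accurate criticism is that the term is unspecified. The subgroup analyses in 9.3 give an informal look at effect modification but do not replace an interaction test.

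Fourth, logistic regression may suit some endpoints. Section 9.2 provides for categorical data, and the heparan sulfate domains may be recorded as present or absent. The fix allows for this.

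**Conclusion.** The point holds as a minor one. Section 9.3 names a method for binary outcomes, applies it to endpoints that are nearly all continuous, and states no responder rule. The cost is at least about 36% of the information, and 42% to 51% at responder shares of 30% down to 20%.

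The 36% should not be read as the plan's own loss. The plan proposes no median split, and that figure is the minimum under normality. The power figures illustrate the cost at assumed correlations, since the documents give none.

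Nothing here weakens the primary t tests or the 23 per group. The point goes beyond missing detail because a better method is available with the same data.

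**What to change.** In 9.3, for continuous endpoints, replace logistic regression with linear regression:

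- **Prognostic factors:** 3-month value on baseline value, arm and factor.
- **Predictive factors:** the same model plus an arm-by-factor term, required before a factor is called predictive.
- **Skewed markers**, such as the albumin/creatinine ratio: analyse on the log scale.
- **Logistic regression:** keep only for endpoints that are truly binary (possibly the urinary heparan sulfate domains) or have a cut-off written down and justified in advance.

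The cost is a few sentences of wording; data and software stay the same. The downside is that interaction tests will have low power with about 23 per arm (about 17% in the example above). They should be reported as exploratory estimates with confidence intervals, and a non-significant interaction should not be taken as evidence that the treatment effect is uniform.
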